## **6.1 Screening (Days –60 to –2)**

Informed consent will be obtained before the following screening tests are conducted:

1. Physical exam with vital signs, including height and weight.
2. Medical history/medication overview.
3. Assessment of ISM symptoms.
4. Blood draw for clinical evaluations:
  - a. Complete blood count with differential (CBC/diff).
  - b. Acute care, hepatic, and mineral panels.
  - c. Serum tryptase.
  - d. Prothrombin/partial thromboplastin time (PT/PTT).
  - e. HIV test (anti-HIV-1/2 antibodies).
  - f. Hepatitis B and C antibody test, B DNA, and C RNA.
  - g. QuantiFERON Gold tuberculosis test.
5. Serum or urine pregnancy test (participants of childbearing potential only).
6. MC-QoL.
7. SCORMA.
8. MSAS.
9. MQLQ/MSAF
10. Bone marrow biopsy and aspirate (if not done at NIH within the last 150 days on protocol 02-I-0277).
11. *KIT* D816V mutation analysis on bone marrow and blood (if not done at NIH within the last 150 days)
12. Flow cytometry on bone marrow and blood (if not done at NIH within the last 150 days).
13. Ultrasound of abdomen.
14. Photography of affected areas.

## **6.2 Randomized, Double-Blinded, Placebo-Controlled Treatment Period**

### **6.2.1 Baseline (Days –2 to 0)**

After eligibility has been confirmed, participants will visit the NIH CC for baseline testing. Participants may be admitted as inpatients and will be randomized to receive sarilumab or placebo. The following procedures will then be done at baseline:

1. Physical exam with vital signs.
2. Overview of medical/medication history.
3. Assessment of baseline symptoms of ISM.

4. Assessment of AEs.
5. Blood draw for clinical evaluations:
  - a. CBC/diff.
  - b. Acute care, hepatic, and mineral panels.
  - c. PT/PTT.
  - d. Total protein.
  - e. Lipid panel.
  - f. Serum tryptase.
  - g. C-reactive protein (CRP).
6. Urine or serum pregnancy test (for participants of childbearing potential only).
7. Blood draw for DNA and RNA collection.
8. Collection of serum (8 mL serum separator tube [SST]) for storage.
9. Serum IL-6 levels.
10. Serum markers of bone marrow resorption and deposition.
11. Plasma for storage (10 mL green top tube [GTT]).
12. Whole blood for storage (3 mL lavender top tube [LTT]).
13. MC-QoL.
14. SCORMA.
15. MSAS.
16. MQLQ/MSAF.
17. *KIT* D816V mutation analysis on blood.
18. Flow cytometry on blood.
19. Photography of affected areas (optional).
20. Skin punch biopsy (optional).

### **6.2.2 First Dose (Day 0)**

Participants will receive either 200 mg of sarilumab or placebo via SC injection (see section 5.4). The participant will be monitored during administration and for 1 hour after to observe for any immediate drug-related AEs. Participants of childbearing potential must have had a negative pregnancy test at baseline before dose administration. Participants will be discharged after postdose monitoring if they have not experienced any serious hypersensitivity reactions. Hypersensitivity reactions will be treated as clinically appropriate. Before discharge, participants will be provided with a side effect and medication change diary (Appendix H), with instructions to fill it out in between visits as appropriate, and to bring it in for review to all future study visit.

### **6.2.3 Doses 2-8 (weeks 2, 4, 6, 8, 10, 12, 14 ± 4 days)**

Participants will return to the NIH CC once every 2 weeks ( $\pm$  4 days) to receive their next dose of study drug or placebo. The exception will be subjects at doses 4, 6, and 8 who have not experienced reactions to the agent. These subjects may opt to self-administer the study agent at home. At each visit where agent will be administered at NIH, before dose administration, the

participant will undergo a physical exam with vital signs, overview of medical history, diary review, and assessment of AEs. At each visits where participants of childbearing potential receive study agent at NIH, they will also have a urine or serum pregnancy test, which must be negative before administration of the study drug. In addition, at the visits for doses 3, 5, and 7 (weeks 4, 8, and 12), participants will undergo the following procedures before dose administration:

1. Blood draw for clinical evaluations:
  - a. CBC/diff.
  - b. Acute care, hepatic, and mineral panels.
  - c. PT/PTT.
  - d. Total protein.
  - e. Lipid panel.
  - f. Serum tryptase.
  - g. CRP.
2. Collection of serum (8 mL SST) for storage.
3. Serum IL-6 levels.
4. Plasma for storage (10 mL GTT).
5. Whole blood for storage (3 mL LTT).
6. MC-QoL.
7. SCORMA.
8. MSAS.
9. MQLQ/MSAF.
10. Photography of affected areas (optional).

As at the first dose visit, participants will be monitored during their injection and for 1 hour after the injection to observe for any immediate drug-related AEs and hypersensitivity reactions. Hypersensitivity reactions will be treated as clinically appropriate.

Participants who have not experienced reactions to the injection after the second dose may, at the request of the participant and the discretion of the PI, be trained to self-inject the study drug/placebo for the fourth, sixth, and eighth doses (weeks 6, 10, and 14). There is no known increase in risks for self injection. Subjects will be provided with dosing materials to take home and instructions for storage and administration. These participants will not have study visits (including pregnancy test, AE evaluation, study diary review or history and physical exam at the NIH for these doses. When a dose is to be self-injected at home, study staff will contact subject to ensure administration took place, and document this in the NIH medical record.

#### **6.2.4 Peak Treatment (Week 16 ± 7 days)**

Two weeks (± 7 days) after the eighth and final dose of sarilumab, the participant will return to the NIH CC and undergo the following procedures. This visit will take 1-2 days, and participants will be seen as outpatients.

1. Physical exam with vital signs.
2. Overview of medical/medication history.
3. Assessment of AEs.
4. Blood draw for clinical evaluations:
  - a. CBC/diff.
  - b. Acute care, hepatic, and mineral panels.
  - c. PT/PTT.
  - d. Total protein.
  - e. Lipid panel.
  - f. Serum tryptase.
  - g. CRP.
5. Urine or serum pregnancy test (for participants of childbearing potential only).
6. Blood draw for RNA collection.
7. Collection of serum (8 mL SST) for storage.
8. Serum IL-6 levels.
9. Serum markers of bone marrow resorption and deposition.
10. Plasma for storage (10 mL GTT).
11. Whole blood for storage (3 mL LTT).
12. MC-QoL.
13. SCORMA.
14. MSAS.
15. MQLQ/MSAF
16. Bone marrow biopsy and aspirate.
17. *KIT* D816V mutation analysis on blood and bone marrow.
18. Flow cytometry on bone marrow and blood.
19. Ultrasound of abdomen.
20. Photography of affected areas.
21. Skin punch biopsy (optional).
22. Diary review.

#### **6.2.5 Post-treatment Visit (Week 28 ± 7 days)**

The participant will return to the NIH CC for a post-treatment visit 12 weeks (± 7 days) after the peak treatment follow-up visit (section 6.2.4). The participant will undergo the following procedures:

1. Physical exam with vital signs.
2. Overview of medical/medication history.
3. Assessment of AEs.
4. Blood draw for clinical evaluations:
  - a. CBC/diff.
  - b. Acute care, hepatic, and mineral panels.
  - c. PT/PTT.
  - d. Total protein.
  - e. Lipid panel.
  - f. Serum tryptase.
  - g. CRP.
5. Pregnancy test (serum or urine, for participants of childbearing potential only).
6. Collection of serum (8 mL SST) for storage.
7. Serum IL-6 levels.
8. Serum markers of bone marrow resorption and deposition.
9. Plasma for storage (10 mL GTT).
10. Whole blood for storage (3 mL LTT).
11. MC-QoL.
12. SCORMA.
13. MSAS.
14. MQLQ/MSAF
15. KIT D816V mutation analysis on blood.
16. Flow cytometry on blood.
17. Photography of affected areas.
18. Diary review.

At the end of this visit, participants who continue to meet all eligibility criteria (sections 4.2 and 4.3) will be offered the opportunity to continue on sarilumab for another 52 weeks. Prior to beginning the open-label treatment, a safety assessment of any AEs that may have occurred during the randomized treatment period will be reviewed with the participant. Participants who decline will end their participation after this visit. Those who accept will continue on the study as described below (section 6.3).

#### **6.2.6 Early Termination Visit**

All effort will be made to conduct an early termination visit for participants who withdraw from the study during the randomized, double-blinded portion. This visit will include all of the procedures performed at the normal peak treatment visit (see section 6.2.4).

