In this study, participants will be randomized with approximately half of the participants receiving study drug, which will be administered at 200 mg via subcutaneous (SC) injection once every 2 weeks (Q2W) for a total of 16 weeks. The other participants will receive a placebo administered via SC injection Q2W for 16 weeks. Participants will return for a follow-up visit 2 weeks after the final dose (treatment peak), and then again 12 weeks later. Evaluations at study visits will include quality of life and symptom assessments and measurement of serum tryptase levels. Bone marrow examination will be performed at the onset and conclusion of the study. After the week 28 visit, all participants will have the option to continue sarilumab for 52 more weeks, at 200 mg administered via SC injections. Participants will continue to be monitored on a regular basis for safety concerns, as instructed in the study drug's package insert.

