### **12.6.3 Discontinuation of Study Agent for Individual Participants**

Permanent discontinuation of study drug will occur per the sarilumab package insert if:

- ANC < 500/mL.
- Platelet count < 50,000/ $\mu$ L.
- ALT > 5  $\times$  ULN

Participants who do not resume study agent during the randomized, double-blind portion of the study will continue to be followed for 16 weeks, and then be encouraged to have an early termination visit (section 6.2.6). Participants who do not resume study agent during the open-label portion will be encouraged to have an early termination visit (section 6.3.3) shortly after the decision is made not to resume.

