AE = adverse event; HBV = hepatitis B virus; HCV = hepatitis C virus; IL = interleukin; ISM = indolent systemic mastocytosis; MC-QoL = Mastocytosis Quality of Life Questionnaire; MSAS = Memorial Symptom Assessment Scale; Q2W = once every 2 weeks; SCORMA = scoring of mastocytosis index; X = to be performed.

A Participants may be admitted as inpatients for this study visit. Procedures will be performed just once during this period.

B At the discretion of the study team, instead of coming to the NIH for study visits on weeks 6, 10 and 14, participants can self-administer study drug at home. No other procedures will be done at these time points for participants who self-administer.

C This visit will take 1-2 days as outpatients.

D Informed consent will be obtained before any study procedures are conducted on this protocol.

E Patients will be randomized to receive sarilumab or placebo.

F The screening physical exam will include measurement of vital signs, height, and weight.

G Sarilumab/placebo will be administered after the other study procedures have been completed.

H Will be done at screening only if not done within the last 150 days on protocol 02-I-0277 or this protocol.

I Only blood will be collected for *KIT* mutation analysis and flow cytometry at these visits.

j Optional at these visits.

k At visits 4, 6, 8, subjects may self inject at home. At these self administered injection timepoints, no assessments will occur.

	Open Administration Visits					Final Study Visit	Early Termination Visit
	Week 1 a	Week 7 ± 7 days	Week 19 ± 14 days	Week 31 ± 14 days	Week 43 ± 14 days	Week 55 ± 14 days	
Procedures/Evaluations							
Physical exam		X	X	X	X	X	X
Medical/medication history		X	X	X	X	X	X
AE assessment		X	X	X	X	X	X
CBC/diff		X	X	X	X	X	X
Acute care, hepatic, and mineral panels		X	X	X	X	X	X
Lipid panel		X		X			
Pregnancy test (serum or urine)		X	X	X	X	X	X
Serum tryptase		X	X	X	X	X	X
Diary review		X	X	X	X	X	X
Memory aid review		X	X	X	X	X	X
Study drug administration b	X	X	X	X	X		

AE = adverse event; CBC = complete blood count.  
 a Week 1 of the open administration portion of this study immediately follows the post-treatment visit.  
 b Study drug will be administered after all other procedures have been completed.

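### The early termination visit asks participants who leave after week 16 to repeat the marrow biopsy and ultrasound, and the text and Appendix A disagree on what is tested on that marrow

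*Combined protocol and SAP*

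**What the plan says.** Section 6.2.6 covers "participants who withdraw from the study during the randomized, double-blinded portion". One sentence fixes the content of their visit: "This visit will include all of the procedures performed at the normal peak treatment visit (see section 6.2.4". The 6.2.4 list includes "Bone marrow biopsy and aspirate", an abdominal ultrasound, and KIT D816V and flow cytometry on both blood and marrow.

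The portion in question is section 6.2, headed "Randomized, Double-Blinded, Placebo-Controlled Treatment Period". Its last scheduled visit is week 28 (section 6.2.5), placed "12 weeks (± 7 days) after the peak treatment follow-up visit". The 6.2.5 list has no marrow and no ultrasound, and takes KIT and flow cytometry on blood only.

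The Précis says: "Bone marrow examination will be performed at the onset and conclusion of the study". Section 6 counts two clinic days with a marrow examination, screening and peak treatment.

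In Appendix A, the early termination column marks the biopsy and the ultrasound with no footnote. The KIT and flow cytometry cells carry footnote i, under which only blood is taken for KIT "mutation analysis and flow cytometry at these visits". Footnote h, which waives marrow work done in the previous 150 days, is attached to the screening column only.

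Under section 12.6.3, participants who stop study agent for good in the double-blind portion "will continue to be followed for 16 weeks, and then be encouraged to have an early termination visit". Section 12.7.3 has nearly the same wording for participants who do not resume after a study halt.

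**The concern.** The early termination list suits someone who leaves before week 16: it captures the end-of-treatment assessments at the last opportunity. The same list is applied to someone who has already had all of those assessments. That person is asked to repeat an invasive research procedure for which section 8.1 acknowledges bleeding, infection and discomfort, plus cardiovascular and respiratory depression where sedation is requested. Nothing in the plan shows what the repeat is for.

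The second problem does not depend on when the participant leaves. Text and table give different instructions about testing the marrow. Staff who follow the table would take a marrow and run neither KIT nor flow cytometry on it. Staff who follow the text would run both.

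At stake are research burden on a few participants and a clear instruction at every early termination visit. The primary estimate, the alpha level and the power are not affected.

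**Working it through.** There is no planned figure to reproduce. The check compares the visit lists and adds simple date arithmetic.

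**1. The lists side by side**

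| Procedure | Week 16 (6.2.4) | Week 28 (6.2.5) | Early termination, text (6.2.6 via 6.2.4) | Early termination, Appendix A |
|---|---|---|---|---|
| Marrow biopsy and aspirate | yes | no | yes | yes, no footnote |
| Abdominal ultrasound | yes | no | yes | yes, no footnote |
| KIT D816V | blood and marrow | blood | blood and marrow | blood only (i) |
| Flow cytometry | blood and marrow | blood | blood and marrow | blood only (i) |
| MC-QoL | yes | yes | yes | yes |

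Text and table agree that marrow is taken at early termination. They disagree on two items, marrow KIT and marrow flow cytometry.

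**2. Does a leaver after week 16 fall under 6.2.6?** Yes. Week 28 is section 6.2.5, inside section 6.2, and 6.2.6 applies to that whole portion. Neither 6.2.6 nor Appendix A makes an exception.

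**3. How recent would the week-16 marrow be?** Assume the early termination visit is held no later than the week-28 window would close.

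- Nominal: (28 − 16) × 7 = 84 days.
- With the 7-day tolerance on the 12-week interval: 84 + 7 = 91 days.
- With both visit windows used in full (week 16 seven days early, week 28 seven days late): 84 + 14 = 98 days.

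All three are below 150 days, the age at which the plan still accepts an existing marrow at screening. By that yardstick the week-16 marrow is always recent, but the waiver is not extended to this visit. For such a participant the repeat is the second marrow after baseline, and the third on this protocol if the screening marrow was also done here.

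**4. Is there a planned use?** The marrow mast-cell endpoint is secondary endpoint 6; liver and spleen size on ultrasound is exploratory endpoint 1. Neither names a time point. Marrow and ultrasound are scheduled only at screening and week 16. A value from weeks 16 to 28 therefore has nothing scheduled to be compared with in other participants, and section 15.5 does not say how a second post-baseline value would be used.

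**5. How many people?** The documents give no rate. Assuming 0 to 10% of the planned 30 leave between weeks 16 and 28: 30 × 0 = 0 to 30 × 0.10 = 3.

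**6. Participants who stop study agent.** Sections 12.6.3 and 12.7.3 do not say when the 16 weeks start.

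- Counted from the first dose, the visit falls at week 16 and can simply be the peak visit: one marrow.
- Counted from stopping at week s, it falls at week s + 16. With doses from week 0 to week 14, that is week 16 to week 30. Anyone who also attended the peak visit would then be asked for marrow twice.

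The text does not choose between these.

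**The case against.** The strongest reply is that the visit is voluntary in practice. Section 6.2.6 promises effort, 12.6.3, 12.7.3 and 12.8 encourage attendance, and consent can be withdrawn at any time. This stands: the documents support saying that participants are asked for a repeat marrow, not that they undergo one.

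A second reply is that the marrow may have a use. The Précis ties marrow to the end of the study, which for a leaver could be the early termination visit; section 7 has marrow read for infiltration, markers and morphology; and consent to storage is required at entry. This also stands in part. That no endpoint needs the repeat is an inference from the schedule, not a statement in the plan. What survives is narrower: the repeat has no scheduled counterpart.

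Three stronger readings are tempting and are not supported:

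- A reader might infer that the marrow requirement deters leavers and costs the trial its primary outcome. Someone who leaves after the week-16 visit would already have given the week-16 MC-QoL. The worry could apply only to those leaving before week 16, whose last value is carried forward under 15.5. Even there, deterrence is plausible but not documented.
- A reader might infer that everyone who stops study agent has marrow twice. Step 6 shows that one marrow is an equally natural reading. Section 12.8 also withdraws anyone missing more than one randomized dose, which could send many early stoppers to this visit before week 16. The wording is ambiguous and shows no more than that.
- A reader might take the Appendix B total as further evidence. The early termination lines sum to 4+4+3+4+10+8+8+4+10+3+1 = 59 mL, against 63 mL printed. That slip is real but has no bearing on the repeat marrow.

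**Conclusion.** The point holds in two parts. First, the written rule asks anyone who withdraws between weeks 16 and 28 for a repeat marrow and ultrasound, at most 98 days after the last ones, with no counterpart in participants who complete week 28. This follows from the text, given that the visit is held by the close of the week-28 window. Second, the text and Appendix A contradict each other on marrow KIT and flow cytometry at every early termination visit in the randomized portion, whatever the dropout rate.

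The size is small: 0 to 3 of 30 on an assumed 0 to 10% leaving after week 16, and possibly nobody. The change is still worth making, because it removes an invasive research request at almost no cost. For participants who leave before week 16, the marrow can serve secondary endpoint 6, and nothing here argues against it.

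**What to change.** 1. In 6.2.6 and the Appendix A early termination column, make the list depend on what has been done. If the week-16 procedures have not been done, use the 6.2.4 list. If they have, use the 6.2.5 list, which has no marrow and no ultrasound.
2. State that MC-QoL, adverse events and safety bloods are collected even if the participant declines marrow. This matters mainly for those leaving before week 16.
3. Reconcile footnote i with 6.2.4 and 6.2.6, so that one instruction says whether marrow taken at this visit goes to KIT and flow cytometry.
4. In 12.6.3 and 12.7.3, state when the 16 weeks start and whether the visit that follows is the week-16 visit or an additional one, and check the result against 12.8.

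The cost is a few sentences and one extra column in Appendix A. What is lost is an unscheduled, unpaired marrow and ultrasound from the few who leave between weeks 16 and 28, along with the RNA draw and optional skin biopsy, which are also absent from the 6.2.5 list. No scheduled endpoint assessment is given up, and no procedure is added.

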### **6.3 Optional Open-label Treatment Period**

For the optional open-label portion of the study, participants will receive 200-mg sarilumab SC Q2W for 52 weeks (26 doses). Participants will be trained by the study team to self-administer the injection at home. The first dose will be given following the post-treatment visit (section 6.2.5), which will be considered week 1 for this portion of the study. Therefore, the final dose will be administered on week 51. The participant will be provided with a memory aid (Appendix I), in addition to the side effect/medication change diary, to keep track of self-administered doses of sarilumab.

For this first dose, the participant will be monitored during administration and for 1 hour after to observe for any immediate drug-related AEs. Participants will be discharged after postdose monitoring if they have not experienced any serious hypersensitivity reactions. Hypersensitivity reactions will be treated as clinically appropriate.

#### **6.3.1 Open Administration Follow-up Visits (week 7 ± 7 days, and weeks 19, 31, and 43 all ± 14 days)**

Participants will return for follow-up visits approximately 6 weeks after starting this treatment period, and every 3 months thereafter. The following procedures will be done at each visit:

1. Physical exam with vital signs.
2. Overview of medical/medication history.
3. Assessment of AEs.
4. Blood draw for clinical evaluations:
  - a. CBC/diff.
  - b. Acute care, hepatic, and mineral panels.
  - c. Serum tryptase
  - d. Lipid panel (weeks 7 and 31 only).
5. Pregnancy test (serum or urine, for participants of childbearing potential only).
6. Diary and memory aid review.

After these procedures, the participant will receive their dose of sarilumab, administered by themselves or by study staff. As at the first open-label dose, participants will be monitored during their injection and for 1 hour after the injection to observe for any immediate drug-related AEs and hypersensitivity reactions. Hypersensitivity reactions will be treated as clinically appropriate.

